Prediction of postsurgical
symptomatic outcomes with
preoperative pessary use

NCT#02680145

08/22/2016

Prediction of postsurgical symptomatic outcomes with preoperative pessary use

Principal Investigator- [name]

Co-Investigator- [name]

Abstract

Pelvic organ prolapse is a highly prevalent and distressing condition for patients. Despite standard office-based consultation many patients report feeling unprepared for surgery. Likewise, in cases of equivocal symptoms, it is difficult to predict the ability of surgery to improve patient's quality of life and meet expectations. Occasionally, some providers utilize a pessary to evaluate the potential role for surgical correction. However, this is an empiric practice, rather than evidence-based. In addition to the evaluation of symptomatic improvement, pessary use in this setting is an important consideration as it may provide a better functional demonstration of the expected postoperative quality of life, compared to office-based discussion. The purpose of this project is to evaluate the potential role of routine pessary placement prior to planned surgery for symptomatic prolapse in a prospective case-crossover trial where patients scheduled for operative prolapse repair will utilize a pessary preoperatively. We anticipate that this trial will define the clinical utility of routine preoperative pessary placement, and by shaping patient expectations and increasing preparedness for surgery, we anticipate improving satisfaction and quality of life.

Research Plan

I. Specific Aims:

Pelvic organ prolapse is a highly prevalent issue in adult women and can have a large impact on a woman's quality of life, leading to discomfort, decreased energy and increase social isolation. Notably, the prevalence of prolapse increases with advancing age and it is estimated that the lifetime risk of a woman undergoing surgery for bothersome prolapse is as high as 13%. Likewise, given the present age distribution in the United States, the number of women seeking treatment for this issue in the future will continue to expand. While many women will undergo surgery, preoperative counseling in preparation for surgery is variable. In fact, self-reported patient preparedness for prolapse surgery has been reported as low as 58% in a previous series from a large tertiary care center. This is an important consideration as patient preparedness for surgery is associated with patient satisfaction and symptomatic improvement.

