Our overall research goal is to evaluate the clinical utility of preoperative pessary placement as a part of patient counseling or preparation for surgery. In this protocol we aim to increase patient preparedness for surgery, patient satisfaction, and post-operative quality of life in adult women scheduled for surgery for symptomatic pelvic organ prolapse. To accomplish this, following counseling regarding all treatment options for prolapse, we will perform a prospective case-crossover study where 112 subjects who elected for surgical management will utilize a pessary for 1-4 weeks prior to undergoing prolapse surgery.

We propose:

Specific aim 1a: To evaluate concordance of the Patient Global Impression of Improvement Score between vaginal pessary use (assessed prior to surgery) and surgical intervention (assessed at 3 months postoperatively) for women with pelvic organ prolapse. *Hypothesis:* There is a strong correlation between the self-reported Patient Global Impression of Improvement Score following pessary use and surgery, as assessed at 3 months post-operatively.

Specific aim 1b.) To evaluate concordance in symptomatic change in pelvic and voiding symptoms (measured by validated symptom questionnaires) from baseline between pessary use (assessed prior to surgery) and surgical intervention (assessed at 3 months postoperatively). *Hypothesis:* There is a strong correlation between the changes in pelvic and voiding symptoms following pessary use and surgery, as assessed at 3 months post-operatively

Specific aim 2: To evaluate the impact of preoperative pessary use on patient preparedness for surgery (measured by validated questionnaire) as compared between the initial office consultation and following 1-4 weeks of pessary use.

Hypothesis: Preoperative pessary use will increase self-reported preoperative patient preparedness for surgery compared to office counseling alone.

II. Research Strategy

1. Significance:

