In pelvic organ prolapse treatment, presently, the pessary test is occasionally empirically used for cases of pelvic organ prolapse with equivocal symptomatology, in order to better inform preoperative counseling and shape patient expectations for prolapse surgery. Interestingly, while this is practiced empirically, there is no evidence available evaluating a correlation between symptom improvement with pessary use and surgical intervention. Thus, if improvement of overactive bladder symptoms, pain or bowel symptoms from pessary use mirrors that of surgery, universal preoperative pessary use may be a low-cost, low-risk, and widely accessible tool for addressing patient's unmet counseling needs.

A.4. Active participation of patients by utilizing a pessary prior to surgery could increase preparedness for surgery.

Despite standard office based preoperative counseling, a previous series from a large tertiary care center reported that only 58% of patients strongly agreed that they were prepared for the surgery. This is an important consideration as patient preparedness for pelvic organ prolapse surgery has been associated with patient satisfaction and subjective symptomatic outcomes, regardless of the anatomic outcome.²

Notably, numerous previous methods for improving patient education for surgery such as hand out leaflets,¹⁹ multimedia presentations,³¹ printing of personalized 3-D models,³² as well as decision aids³³ have been studied with mixed results. While these methods may potentially improve patient knowledge of the anticipated surgery, none allow for a demonstration of functional outcomes. As such, universal use of a pessary preoperatively, could uniquely improve patient preparedness for surgery by demonstrating the potential functional result of surgery.

B. Innovation

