The proposed project is a new approach to addressing the gaps in patient counseling and preparedness for surgery that currently exist. The proposed protocol will clarify the utility of pessary placement given the noted heterogeneity in current clinical practices. Additionally, while pessaries are at times used clinically to help differentiate potential symptoms that may improve with surgery, this is an empirical rather than evidence-based practice. Thus, correlation of symptomatic change in bladder, bowel or pain symptoms with pessary use and surgery is important for pre-operative counseling. Additionally, with recent evidence regarding the importance of preoperative patient preparedness on surgical outcomes and patient satisfaction, evaluating the use of a pessary as part of patient education and preoperative preparation may highlight a potential innovative, low-cost, low-risk, and widely accessible tool for improving patient care and obtaining the best experience for our patients.

C. Approach- Experimental Design and Methods:

C.1. Study design and overview

Overview: This is a single center, prospective, case-cross over trial of pessary use prior to reconstructive pelvic floor surgery for pelvic organ prolapse. The goal of the study is to evaluate the comparative efficacy of pessary use on pelvic floor symptoms versus surgical correction. Additionally, we will assess the impact that preoperative pessary use has on patient self-reported preparedness for surgery.

Study procedure and design: All patients will undergo baseline symptom evaluation via validated questionnaire at the time of their initial office consultation. Following this, the patient will undergo pessary fitting at least 7 days prior to scheduled surgical prolapse repair. The pessary will be left in place and symptomatic change from baseline assessed via validated questionnaire roughly 4 weeks after use or immediately prior to surgery (i.e. with the pessary in place). The pessary will then be removed at the time of surgery, and the patient will undergo surgical correction of their pelvic organ prolapse (including all restorative surgical procedures, abdominal and transvaginal). A concomitant anti-incontinence procedure will be performed at the discretion of the treating physician in consultation with the patient. The patient's symptomatic

outcome from surgery will then be reassessed by validated questionnaire at 6 weeks and 3 months postoperatively. (See Study Design Flow Chart)

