Carry-Over Effect: This would be encountered if preoperative pessary use changed the pelvic floor in a way that influenced the outcome of surgery. As there is no “wash-out” time from pessary removal to surgery, such an effect would impact the surgical outcome. Given that the pessary is a mechanical change in anatomy of the pelvic floor, we anticipate that with pessary removal there would not be residual impact from the pessary.

Recruitment: As patients would be counseled regarding surgery and pessary use and would have elected for surgery prior to study consent, we could encounter difficulties with recruitment in that patients would need to consent to temporary pessary use. Given the volume of patients seen in our department and the sample size needed, we feel that this should not be prohibitive.

Alternative strategies:

Observational cohort: An alternative strategy would be to compare symptomatic improvements between pessary use and surgery in two separate cohorts of patients, in an observational study. As there would be

significant selection bias in patients that undergo pessary placement rather than surgical correction, this methodology was not preferred.

Randomized clinical trial: A randomized clinical trial could be performed where patients are randomized to preoperative pessary use or proceeding directly to surgery. This approach could potentially minimize the impact of confounding variables. This method was not preferred due to perceived difficulty in recruitment (as patients may have a specific time in which they prefer to have surgery) and difficulty in surgical scheduling.

C.7. Timeframe: (24 months)

For Aim 1, we estimate that it will take 8 months for recruitment of the 62 patients, assuming a recruitment rate of 15% (~54 surgeries for prolapse in our division per month, as estimated by averaging volume from 2013 and 2014). For completion of Aim 2, we estimate that it will take 14 months to recruit the 112 patients for study, assuming a recruitment rate of 15%. Given the surgical volume in our division we anticipate being able to meet the accrual requirements.

	2016							2017											2018					
Study Month	1	2	3	4	5	6	7	8	9	10	11	12	13	14	15	16	17	18	19	20	21	22	23	24
Aim 1																								
Data Collection	x	x	x	x	x	x	x	x																
Data Analysis									x	x														
Manuscript										x	x	x	x											
Aim 2																								
Data Collection	x	x	x	x	x	x	x	x	x	x	x	x	x	x										

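### The fixed pessary-then-surgery sequence cannot support the comparative-efficacy goal in C.1, and C.6 sets carry-over aside on mechanical grounds only

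*Combined protocol and SAP*

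**What the plan says.** C.1 states the purpose in comparative terms: "The goal of the study is to evaluate the comparative efficacy of pessary use on pelvic floor symptoms versus surgical correction". A.2 likewise presents the protocol as a comparison of improvement under the two treatments.

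The design has one sequence. Under Specific Aims, "112 subjects who elected for surgical management will utilize a pessary for 1-4 weeks prior to undergoing prolapse surgery"; in C.1, "The pessary will then be removed at the time of surgery". C.2 makes electing surgical repair an inclusion criterion and excludes women previously managed with a pessary.

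On carry-over, C.6 gives this definition: "This would be encountered if preoperative pessary use changed the pelvic floor in a way that influenced the outcome of surgery". It concedes that there is no wash-out "time from pessary removal to surgery, such an effect would impact the surgical outcome". It then sets the matter aside because the pessary acts mechanically: "we anticipate that with pessary removal there would not be residual impact from the pessary".

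Elsewhere the plan relies on a pathway that is not mechanical. The Abstract says that "by shaping patient expectations and increasing preparedness for surgery, we anticipate improving satisfaction and quality of life". A.4 adds that "patient preparedness for pelvic organ prolapse surgery has been associated with patient satisfaction and subjective symptomatic outcomes, regardless of the anatomic outcome". The Specific Aims list better quality of life after surgery among the things the protocol is meant to achieve.

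The analysis paragraph in C.5 compares post-pessary with post-surgery responses by McNemar's test (dichotomous) and Bowker's test (ordinal), two-sided at 0.05. It also gives percent concordance with a 95% confidence interval and Lin's coefficient for the summary scores.

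**The concern.** The C.6 argument covers only one route by which an earlier treatment can affect a later outcome. The PGI-I, POPDI-6, PFIQ-7 and OABSS are all completed by the patient, so a change in expectations can alter the post-surgery answer without any change in the pelvic floor. The plan's own rationale is that the pessary changes expectations.

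Two misreadings are possible. A significant McNemar or Bowker result, read against the goal in C.1, would look like evidence that one treatment outperforms the other. Order, treatment preference and expectation could produce the same result. Good agreement could be taken to show that the two treatments correct the same symptoms, when the pessary experience may have helped to set the later rating.

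**Working it through.** **1. The plan's own figures.** These reproduce and are not in dispute.
- Aim 1 (C.4: 80% concordance, half-width 10 points): n = 1.96² × 0.8 × 0.2 / 0.1² = 61.5, rounded up to 62. The stated interval of 70.8–90.5% is the Wald interval for 50/62.
- Aim 2 (C.4: 58% to 75%, correlation 0.30): P(prepared both times) = 0.58 × 0.75 + 0.30 × √(0.58 × 0.42 × 0.75 × 0.25) = 0.499. The discordant cells are 0.75 − 0.499 = 0.251 and 0.58 − 0.499 = 0.081. The uncorrected McNemar test at n = 84 has 80.8% power by enumeration, against the stated 80%.
- Drop-out: 84 / 0.75 = 112.

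**2. What the design identifies.** Write P for the pessary response, S for the response to surgery without a prior pessary, and c for any effect of prior pessary use on the post-surgery rating. The data give P and S + c. The paired difference therefore estimates (S − P) + c, together with any effect of period. No group supplies S alone and no reverse sequence exists, so c cannot be separated from S − P. All these women also preferred surgery to a pessary, so the contrast applies to that selected group.

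**3. The passages side by side.** C.6 takes c = 0 because nothing physical remains after removal. The Abstract and Specific Aims expect c ≠ 0 for satisfaction and quality of life. A.4 supplies the link, from preparedness to subjective outcome, and says it does not run through anatomy. The two positions can both hold only if carry-over is restricted to anatomy, and no Aim 1 outcome is anatomical.

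**4. Illustration of scale.** The documents give neither c nor a success rate for either treatment, so these inputs are assumptions: equal true success P = S, paired correlation 0.30, n = 84, and c added to post-surgery success. For example, with P = 0.80 and c = 0.10, P(success both times) = 0.80 × 0.90 + 0.30 × √(0.16 × 0.09) = 0.756. The discordant cells are 0.044 and 0.144, and binary concordance is 1 − 0.188 = 81.2%. The chance that McNemar's test reports a difference is:

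| Assumed c | Success 60% | Success 70% | Success 80% |
|---|---|---|---|
| 0 | 5% | 5% | 5% |
| 5 points | 13% | 14% | 17% |
| 10 points | 37% | 44% | 58% |
| 15 points | 71% | 81% | 96% |

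Concordance moves much less. From c = 0 to 15 points it goes from 66.4% to 67.7% (success 60%), 70.6% to 73.8% (70%) and 77.6% to 82.2% (80%). In this illustration the difference tests are the exposed part of the analysis. The table takes c as positive, and the documents do not establish its sign.

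**The case against.** The study is titled and sized as a prediction study. Aims 1a and 1b are concordance aims, C.3 estimates concordance, and the 62 patients are set by its precision. The practice under evaluation is routine pessary use before surgery, so surgery after a pessary is the relevant condition, and an expectation effect is arguably part of that strategy. C.5 does not call McNemar's or Bowker's test an efficacy test. C.6 admits the missing wash-out, mentions that women elected surgery before consent, and considers randomizing to pessary or direct surgery, rejecting it as hard to recruit and schedule. All of this stands, and it limits the point to the comparative goal and the difference tests.

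A reader might go further in three ways that the documents do not support.
- **That Aim 1 is invalid.** Concordance in women who chose surgery and used a pessary first remains estimable, and it is useful for preoperative counselling.
- **That the pessary alters the post-surgery rating in every woman.** A.4 reports an association from a cited study. Even if Aim 2's hypothesis is true, the link would also have to be causal.
- **That Aim 2's inputs give the size of the effect on concordance.** They imply that about 28 of 84 women change their preparedness answer (0.332 × 84). Seven of these move away from strong agreement, and the net gain is only 14 (0.17 × 84). Nothing says how many would rate surgery differently, or in which direction.

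A check of concordance by change in preparedness would not settle the matter. About 42 of the 56 women expected to be unchanged (0.499 × 84) strongly agree both times and are at the ceiling of the scale. The stratifier is measured after pessary use and may itself reflect pessary response. At 80% concordance in both groups, the 95% half-width for 28 against 56 women is 1.96 × √(0.16/28 + 0.16/56), or about 18 points.

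**Conclusion.** The point holds for the comparative-efficacy goal in C.1, the matching statement in A.2, and any inferential reading of the post-pessary versus post-surgery tests in C.5. The estimable contrast is pessary versus surgery after pessary, in women who preferred surgery. The no-residual-impact statement in C.6 is inconsistent with the rationale in the Abstract, Specific Aims and A.4. This conclusion rests on the fixed order, the absence of a direct-to-surgery group and the self-reported outcomes, all of which are in the text.

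The direction and size of the carry-over cannot be derived from the documents; the table above shows only what assumed values would do. Aim 2 compares preparedness before and after pessary use and is complete before surgery, so this carry-over does not reach it. No sample size changes. The correction should be made, but it does not call for a redesign: surgery cannot be reversed, so a reverse-order period is unrealistic.

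**What to change.** 1. In C.1, and in the corresponding sentence of A.2, restate the goal as within-woman agreement between the response to a pessary and the later response to surgery, in women who chose surgery and used a pessary first.
2. In C.5, label the post-pessary versus post-surgery McNemar and Bowker results descriptive, and state that they do not test comparative efficacy. McNemar's test for Aim 2 preparedness is not affected.
3. In C.6, limit the mechanical argument to anatomical carry-over. Add that expectation-mediated carry-over, and the selection of women who preferred surgery, cannot be separated from the treatment contrast.

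The changes are to wording only, with no added patients, visits or questionnaires. The price is that the study gives up a claim about the efficacy of pessary relative to surgery, which this design could not support.

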Aim 1: Using the 7-point Likert scale of the PGI-I, we anticipate an overall concordance of at least 80% between the within patient ratings following pessary use and 6-weeks following surgery after collapsing the categories into a) much better or very much better, b) a little better, no change, or a little worse, or c) much worse or very much worse. In order to estimate the concordance with a ½ width of the 95% CI of 10% (i.e. 95% CI of 70.8-90.5%), the study will need 62 patients.

Aim 2: Based on a recent study of 79 women who underwent reconstructive pelvic surgery after standard office counseling, 58% strongly agreed that they were prepared for their upcoming surgery.² If we assume that following pessary use, 75% will endorse that they strongly agreed that they were prepared for their upcoming surgery, then the study will have 80% power to detect this difference with a sample size of 84 patients. This calculation was based on two-sided McNemar's test for comparing correlated proportions assuming a mild correlation (0.30) between the paired measures and a type I error of 0.05. Assuming a conservative 25% drop-out rate (failure to wear the pessary or complete follow-up questionnaires) then the study would need to consent 112 patients.

Feasibility: The Division of Urogynecology at Mayo Clinic, Rochester, MN typically performs roughly 1350 surgeries annually (averaged from surgical volume from 1/1/2013 to 1/1/2015). Among those, the four fellowship trained Urogynecologists typically perform roughly 650 prolapse procedures per year. Thus, given the large surgical volume, recruitment for this study is feasible as a single center trial.

C.5. Data Collection

Preoperative demographic data, complete medical and surgical histories, as well as current medications and allergies will be obtained to ensure patients meet inclusion and exclusion requirements. Participants will fill out the following validated questionnaires and questions prior to any intervention and following each

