treatment (pessary and surgery): Pelvic Floor Impact Questionnaires (PFIQ-7),³⁷ Pelvic Organ Prolapse Distress Inventory 6 (POPDI-6),³⁷ and Overactive Bladder Symptom Score (OABSS).³⁸ Thus, questionnaire assessments will be completed at the time of initial consultation, immediately prior to surgery (after pessary use), at 6 weeks postoperatively during office consultation, and via mailed questionnaires and phone interviews at 3 months. Patient preparedness for surgery will be assessed via validated questions after completing the standard office based counseling and signing the surgical informed consent (prior to pessary use), as well as immediately prior to surgery (after pessary use), according to validated questions evaluating self-reported preparedness for pelvic surgery.² Furthermore, following treatment with a pessary (prior to surgery), at 6 weeks and 3 months after surgery patients will complete the Patient Global Impression of Improvement (PGI-I) question.^{1, 35} All adverse events associated with pessary use or surgery will be documented and abstracted.

Baseline characteristics for the patients included in the trial will be reported as median with inter-quartile range for continuous variables and counts with percentages for categorical variables. The percent concordant will be calculated along with the corresponding 95% confidence interval. Given the paired nature of the data (post-pessary vs. post-surgery), differences between the two time points for dichotomous responses will be assessed using McNemar’s test whereas differences between ordinal responses will be assessed using Bowker’s test for symmetry. The correlation between the two time points for summary scores from validated questionnaires (POPDI-6, PFIQ-7, OABSS) will be assessed using Lin’s concordance correlation coefficient. All calculated p-values will be two sided and will be considered significant if < 0.05.

Study Schedule	Initial visit	After pessary use, day of surgery	Surgery	6 wks after surgery (clinic visit)	3 mos after surgery (mailing)
Medical History and Physical	X				
Informed Consent	X				
Pessary Fitting	X				
Preparedness for Surgery	X	X			
PFIQ-7	X	X		X	X
POPDI-6	X	X		X	X
OABSS	X	X		X	X
PGII		X		X	X
Surgery			X		

C.6. Potential limitations of the study design and alternative strategies:

Potential Limitations:

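### C.7 treats the 62 rated pairs that C.4 requires for Aim 1 as 62 women to recruit, and its chart shows no follow-up time before the Aim 1 analysis

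*Combined protocol and SAP*

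**What the plan says.** - **C.4, Aim 1.** Concordance of at least 80% on a three-category PGI-I is anticipated "between the within patient ratings following pessary use and 6-weeks following surgery". The paragraph closes with "i.e. 95% CI of 70.8-90.5%), the study will need 62 patients". It mentions no drop-out.
- **C.4, Aim 2.** The 84 women needed become 112 to consent: "Assuming a conservative 25% drop-out rate (failure to wear the pessary or complete follow-up questionnaires".
- **Section I.** There is one study: "112 subjects who elected for surgical management will utilize a pessary for 1-4 weeks prior to undergoing prolapse surgery". Specific aim 1a compares pessary use "and surgical intervention (assessed at 3 months postoperatively) for women with pelvic organ prolapse".
- **C.5.** After the pessary rating, "at 6 weeks and 3 months after surgery patients will complete the Patient Global Impression of Improvement (PGI-I) question". For the analysis, "The percent concordant will be calculated along with the corresponding 95% confidence interval". Neither a number of women nor a data cut is given.
- **C.7, text.** "For Aim 1, we estimate that it will take 8 months for recruitment of the 62 patients, assuming a recruitment rate of 15" percent. The next sentence gives 14 months for the 112 at the same rate.
- **C.7, chart.** Aim 1 data collection runs in months 1-8, analysis in months 9-10 and the manuscript in months 10-13. Aim 2 data collection runs to month 14.

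**The concern.** The number of analysable pairs and the number to recruit are different quantities. C.7 puts an uninflated 62 beside a 112 that already includes 25% loss and treats both as enrolment targets. The 25% appears only under Aim 2, but its stated causes apply at least as much to Aim 1. Under the C.5 schedule, preparedness (Aim 2) is last measured on the day of surgery, whereas Aim 1 needs the same pessary wear and also a rating after surgery.

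The chart adds to this. Aim 1 data collection stops in the month in which recruitment of the 62 stops. A woman enrolled then still has 1-4 weeks of pessary use ahead, followed by 6 weeks or 3 months of follow-up. Aim 1 analysis and manuscript are both charted before recruitment of the 112 ends, and nothing says which women that report would use.

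Aim 1a is the primary aim and the width of its interval is its only stated design target, so an analysis made as charted could miss that target.

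**Working it through.** **Inputs.** Concordance 80% and half-width 10 points (C.4, Aim 1); drop-out 25% (C.4, Aim 2); about 54 prolapse surgeries a month and 15% recruitment (C.7); pessary use 1-4 weeks (Section I); rating at 6 weeks (C.4) or 3 months (Aim 1a). Assumptions of this check: even accrual from month 0, pessary use starting at enrolment, 4.35 weeks per month. Pessary use is then 0.23-0.92 months and 6 weeks is 1.38 months.

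**1. The plan's own figures reproduce.**
- n = 1.96² × 0.80 × 0.20 / 0.10² = 61.5, so 62.
- 50/62 = 0.8065; 0.8065 ± 1.96 × √(0.8065 × 0.1935 / 62) gives 70.8% to 90.5%, the interval in C.4. So 62 is a count of women with both ratings.
- Accrual: 54 × 0.15 = 8.1 a month; 62/8.1 = 7.65 months (C.7: 8) and 112/8.1 = 13.83 months (C.7: 14).
- 84/0.75 = 112.

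**2. 62 recruited, all followed up.** Half-width = 1.96 × √(0.16/n).

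| Loss | Pairs | Half-width (points) |
|---|---|---|
| 0% | 62 | 10.0 |
| 5% | 58.9 | 10.2 |
| 10% | 55.8 | 10.5 |
| 25% | 46.5 | 11.5 |

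**3. When the 62nd woman is complete.**
- 6-week rating: 7.65 + (0.23 to 0.92) + 1.38 = month 9.3 to 9.95.
- 3-month rating: 7.65 + (0.23 to 0.92) + 3 = month 10.9 to 11.6, after the charted analysis has ended.

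**4. Data accepted to the end of month 10 from everyone enrolled.** Women who could have the rating = 8.1 × (10 − pessary time − follow-up).
- 6-week: 8.1 × (10 − 0.92 − 1.38) = 62.4 to 8.1 × (10 − 0.23 − 1.38) = 68.0. After 25% loss, 46.8 to 51.0 remain (±11.5 to ±11.0).
- 3-month: 8.1 × (10 − 0.92 − 3) = 49.2 to 8.1 × (10 − 0.23 − 3) = 54.8 before any loss (±11.2 to ±10.6).

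**5. Full study.** 112 × 0.75 = 84 pairs; 1.96 × √(0.16/84) = 0.0855, about ±8.6 points. Follow-up of the 112th woman ends at 13.83 + (0.23 to 0.92) + 1.38 = month 15.4 to 16.1 (6-week), or with + 3 in place of 1.38, month 17.1 to 17.8 (3-month).

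**The case against.** **C.7 is a feasibility projection.** It sets no analysis set and no data cut. The Aim 2 bar also stops when recruitment stops, so both bars may simply track enrolment. This stands, and it rules out reading the chart as a planned cut at month 8. It does not explain an analysis charted to end in month 10.

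**The manuscript row runs to month 13.** If data were accepted until then, 25% loss would leave 65-69 six-week pairs (about ±9.7 to ±9.4), which meets the C.4 target, or 55-59 three-month pairs (about ±10.6 to ±10.2). This is fair, but it means adding data after the charted analysis, which the plan does not say.

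**The effect is small.** The plan calls 25% conservative and expects at least 80% concordance. At 86%, 46.5 pairs still give 1.96 × √(0.86 × 0.14 / 46.5) = ±10.0 points. This stands and limits the weight of the point.

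**Stronger readings that the documents do not support:**
- A reader might infer that the study is too small for Aim 1. It is not. Section I and C.4 describe one study consenting 112, and C.5 restricts the concordance analysis to no subset.
- A reader might infer a tolerable loss of about 1-9% (1 − 62/62.4 to 1 − 62/68.0). That applies only if women enrolled after the 62nd count up to month 10. If only 62 are recruited, the tolerable loss is zero.
- The shortfall on the 3-month rating owes much to the separate conflict between C.4 and Aim 1a, and should not all be charged to the chart.

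**Conclusion.** The point holds, at minor severity. The arithmetic in C.4 is right. C.7 uses its result as a different quantity and charts the Aim 1 analysis too early to deliver it. An Aim 1 analysis completed by month 10 would not reach 62 pairs on the 6-week rating at the plan's own 25% loss. On the 3-month rating it would not reach 62 even with no loss. The cost is a half-width of about 11.5 points instead of 10 for 62 recruited with 25% lost. Aim 1a is an estimation aim, so no test or power is affected, and the complete study gives better precision than C.4 asks for.

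The half-widths assume 80% concordance and that the 25% applies to Aim 1 pairs. The month-10 counts also assume even accrual, 1-4 weeks from enrolment to surgery, and a data cut at the end of month 10, which the plan does not state.

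**What to change.** Three text changes:

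1. In C.4 and C.7, state that the Aim 1 analysis uses all consented women with both PGI-I ratings once their follow-up is complete: 112 consented, about 84 pairs, 95% CI about ±8.6 points at 80% concordance.
2. Reconcile the Aim 1 rating time between C.4 (6 weeks) and Specific aim 1a (3 months).
3. In the C.7 chart, extend Aim 1 data collection to the end of that follow-up, roughly month 16 for the 6-week rating or month 18 for the 3-month rating, and start the analysis after it.

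If an early report on the first 62 recruited is wanted, say so, restate its half-width as about ±11.5 points at 25% loss, and cut the data only after their follow-up.

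No extra women or visits are needed. The cost is a later Aim 1 report. The chart allows 5 months from the end of Aim 1 data collection (month 8) to the end of its manuscript (month 13). Keeping that interval, Aim 1 would finish at about month 21 (16.1 + 5) or month 23 (17.8 + 5), within the 24-month plan.
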